### ***Protocol deviations***

During the review of the database, compliance with the protocol will be examined with regard to inclusion and exclusion criteria, treatment, prohibited therapies, and timing and availability of planned assessments. Protocol deviations will be identified by the study team before database lock and classified as minor, major or critical deviations, in consideration of whether this could potentially affect efficacy assessment endpoints. A listing of major or critical protocol deviations for all treated patients will be produced.

In addition to the above, the two conditions listed below will be evaluated:

**Noncompliance:** Missing 4 or more infusions for each 12 month period in this study, excluding for-cause missed infusions (such as when the missed infusions are required by the protocol due to a dose limiting toxicity), calculated over the extension phase only. Whether a missed infusion is for-cause or not will be reviewed and determined by the clinical team; the decision will be used in the determination of noncompliance. For details of calculations, please refer to [Section 2.4.6.2](#).

**Prohibited medications intake:** The prohibited medications in this study have been defined in [Section 2.1.2](#). The prohibited medication use that could potentially modify the effect of olipudase alfa (which includes, but not limited to, certain antidepressant) or could threaten the safety of olipudase alfa are major protocol deviations.

The protocol deviations identified by the review of the above two conditions will be listed for all treated patients as protocol deviations.

## **2.3 ANALYSIS POPULATIONS**

### **2.3.1 Safety population**

All subjects who were exposed to the study treatment, olipudase alfa, ie, who received at least one infusion of study treatment (total or partial), will be included in the safety population.

### **2.3.2 Pharmacokinetic population**

The pharmacokinetic population includes all patients who receive at least 1 infusion of olipudase alfa and have evaluable pharmacokinetic data available post-baseline.

### **2.3.3 Pharmacodynamic population**

Pharmacodynamic population includes all patients who are treated and have at least one evaluable pharmacodynamic measurement available post-baseline.

## **2.4 STATISTICAL METHODS**

Data collected in this study will be presented using summary tables, figures, and data listings. Descriptive statistics for categorical variables will be provided using frequencies (n) and percentages (%). Descriptive statistics for continuous variables will be provided using number of observations (n), mean, standard deviation (SD), median, minimum, and maximum. All data used in tabular summaries or figures will be supported by listings of underlying data – raw and/or derived, and all figures will be supported by relevant summary information.

All summaries will be provided for the LTS population, along with separate subgroups in the population according to which original study the patient belonged to: DFI13412 (adult study, Phase 1B, 26 weeks, 5 patients), DFI13803 (pediatric study, Phase 1/2, 64 weeks, 12 patients). In addition, similar summaries will be produced by age cohort of adolescent, child, infant for the patients who transition from pediatric study DFI13803.

The scheduled visits in statistical displays will be labelled in months of total follow up time from the first infusion in the original study. For example, a 6-month visit in this study for a patient transitioning from the 26-week DFI13412 study will be identified as Month 12 exposure in the displays. The schedule of measurements for this study will be followed for display presentation with baseline derived from the original study. For patients in this study, the results from the original study visits will be included, unless specified otherwise, for the purpose of understanding the continuity of treatment effect during this extension phase; for details and descriptions of all results from the original study, please refer to the original study CSR. For parameters that are not collected in the extension phase will not be part of this SAP.

#### **2.4.1 Demographics and baseline characteristics**

Demographic and baseline characteristics, medical history and smoking/alcohol history from original study will be summarized using the safety population.

Genotype of acid sphingomyelinase gene (SMPD1), CHIT1, UGT1A1 will also be summarized with baseline disease characteristics, and be provided in data listings.

The SMPD1 variant type (ie, missense, frameshift, deletion, nonsense, etc) will be derived, if possible, from the SMPD1 amino-acid change.

For the classification of CHIT1 genotype, the following derivation will be applied:

- N = Wildtype (WT)/WT = Normal / 2 functional alleles
- H = WT/Duplication 24 (DUP24) = Heterozygous mutation / 1 functional allele
- M = DUP24/DUP24 = homozygous mutation / 2 non-functional alleles (no chito activity)

For the classification of UGT1A1 genotype, the following derivation will be applied:

- UGT1A1\*1 = Fully functional allele = Not Gilbert variant
- UGT1A1\*36 = Functional allele = Not Gilbert variant
- UGT1A1\*28 = Gilbert syndrome allele = Gilbert variant
- UGT1A1\*37 = Crigler-Najjar syndrome type 2 allele (impaired UGT1A1) = Gilbert variant

Patients with 0 or 1 Gilbert variant alleles will be classified as “no Gilbert Syndrome”; patients with 2 Gilbert variants alleles will be classified as “Gilbert Syndrome”.

#### **2.4.2 Baseline safety parameters**

Baseline for safety parameters (weight, height, body mass index (BMI), physical exam, vital signs, echocardiograms, immune response assessments, and safety biomarkers) in general is defined as the last available non-missing value for the parameter before the first infusion in the original study. Most of the baseline values will thus be from the Day 1/Week 0 pre-infusion assessments in the original study, with the exception of hematology parameters and possibly electrocardiogram (ECG). Hematology samples are collected for pediatric patients twice at screening and twice on first infusion visit, once before and once after the first infusion; for adult patients, they are collected once at screening, twice before infusion on first infusion visit and one after the first infusion. The average of all measurements taken before the first infusion will serve as the baseline. Another exception may be the ECG parameters – Day 1/Week 0 (the first infusion visit in the original study) is to collect ECG in triplicate before the infusion; if 2 or more than 2 of these triplicate collections of ECG are before the first infusion, the average of these ECG parameter results will be considered as the baseline value; otherwise, the baseline value of ECG parameters will be taken from the latest observation before the first infusion.

Baseline safety data will be presented along with subsequent values assessed during or after olipudase alfa dosing using safety population.

#### **2.4.3 Baseline efficacy parameters**

Baseline for efficacy parameters (spleen/liver volume, pulmonary function, pulmonary imaging, cycle ergometry, efficacy biomarkers, height z-score, bone disease assessments, etc) is defined as the last available non-missing value for the parameter before the first infusion in the original study, except for the hematology parameters; for complete definition of baseline derivation, please refer to [Section 2.6.1](#)

#### **2.4.4 Baseline pharmacodynamic parameters**

Baseline values for sphingomyelin and sphingomyelin metabolites, including, but not limited to, ceramide in dried blood spots (DBS), lyso-sphingomyelin and sphingosine-1-phosphate in both plasma and DBS will be the last available value before first infusion in the original study; typically these will be the screening values from the original study.

Baseline pharmacodynamic data will be presented along with subsequent pharmacodynamic values assessed during or after olipudase alfa dosing using pharmacodynamic population.

#### **2.4.5 Prior or concomitant medications**

Concomitant medications have been defined in [Section 2.1.2](#). In case the start/stop date of the medication is missing or incomplete preventing the unambiguous determination of the medication status, the medication will be categorized as concomitant.

Medication summaries will be presented by WHO-DRUG Anatomic Class and by WHO-DRUG Therapeutic Class using safety population. Tables will show all medications used during the study, sorted by most prevalent Anatomic Class and then by descending frequency of Therapeutic Class within Anatomic Class based on the prevalence within the overall column.

The prohibited medications in this study have been defined in [Section 2.1.2](#). The list of prohibited antidepressant medications will be provided by the data management and will be merged with the concomitant medication data in the database to identify any use of it. For the cationic amphiphilic antihistaminics where an exhaustive list of drugs cannot be provided, clinical review performed before the database lock will determine whether their use constitutes a protocol deviation that interferes with assessment of effect of olipudase alfa. For the medications prohibited before and after the liver biopsies where an exhaustive list of drugs cannot be provided, clinical review performed before the database lock will determine whether their use constitutes a protocol deviation that interferes with assessment of the safety of olipudase alfa. A data listing of prohibited medication including antidepressant use, and any medication use identified in the clinical review as protocol deviation, will be provided, and will be identified with the respective category.

## **2.4.6 Extent of investigational medicinal product exposure and compliance**

### **2.4.6.1 Extent of investigational medicinal product exposure**

The extent of study treatment exposure will be assessed from the first infusion in the original study, and will be summarized using safety population. The duration of exposure is defined as the number of weeks between first infusion in the original study and disposition date in the study: (disposition date of the study [or the cutoff date for database lock if the patients are still ongoing] – first infusion date from original study + 1)/7. The number of infusions received and the duration of exposure will be summarized using safety population.

The distribution of weeks on study treatment (<12 weeks, >=12 weeks to <26 weeks, >=26 weeks to <38 weeks, >=38 weeks to <52 weeks, >=52 weeks to <64 weeks, etc) will be provided using number and percentage of patients by age group cohorts and overall. The total number of patient-years of exposure will also be provided.

Any overdose will be captured as an AE, and will be reported as such.

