7 SELECTION OF PATIENTS

7.1 INCLUSION CRITERIA

To enter this study, patients must have fulfilled the following criteria:

- I 01. The patient completed the treatment period of a previous study of olipudase alfa with an acceptable safety profile in the opinion of the investigator and sponsor.
- I 02. The patient and the patient's parent(s)/legal guardian(s) is willing and able to provide signed written informed consent.
- I 03. The patient who is female and of childbearing potential must have a negative urine pregnancy test for beta-human chorionic gonadotropin (β-HCG) (see [Section 9.1.9](#)).
- I 04. Female patients of childbearing potential and sexually mature male patients must be willing to practice true abstinence in line with their preferred and usual lifestyle or use 2 acceptable effective methods of contraception up to 15 days following their last dose of study drug (see [Section 10.2.3.2](#)).

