11.3 DISPOSITION OF PATIENTS

Enrolled patients are defined as patients who signed informed consent forms.

Patient enrollment will be summarized for the enrolled patient set by study site, including frequency and percentage of patients who received at least 1 infusion (total or partial) of study treatment.

All patients who receive an infusion (total or partial) of olipudase alfa (safety population) will be included in the summary of patient disposition. The number and percentage of patients who either complete the study or withdraw from the study, and/or withdraw from treatment, along with the

reasons for their withdrawal, and who completed or discontinued the posttreatment safety follow up will be presented.

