#### **2.1.3.2 Deaths**

The death observation periods are defined below:

- Death on-treatment: deaths occurring during the treatment epoch.
- Death on-study: deaths occurring between informed consent date in this study and the end of the study.

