## 2.2 DISPOSITION OF PATIENTS

This section describes patient disposition for patient study status.

Enrolled patients are those who signed the informed consent for this study and met all enrollment criteria for this study. Number and percentage (calculated based on the number of patients who have completed the treatment period of the original study on schedule) of enrolled patients will be provided. Patients who have received one infusion of olipudase alfa in this extension phase, those who are continuing in the study at the time of reporting, those who completed the study and those who prematurely discontinued the study will be summarized; percentage will be calculated based on the number of enrolled patients. The reason for premature discontinuation will also be provided.

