- Action taken towards study drug and action taken (toward AE) will be considered in relation to the date the event became serious, the last infusion date and dosing information, and a determination will be made, in consultation with safety monitor of the trial, as to whether the recorded fields belong to non-serious AE or serious AE; then the decision will be implemented in analysis. Any such decision will be rationalized in the CSR.

For treatment-emergent AEs, separate listing of AEs, SAEs and IARs that started only after the first infusion in this extension study will be provided.

Start day of treatment emergent AE relative to first infusion = Start date of AE – first infusion date + 1

Start day of treatment emergent AE relative to last infusion = Start date of AE – last infusion date + 1

Total patient year for each group will be calculated and displayed on selected AE tables.

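### The SAP's only patient-year total starts at the first original-study infusion, so it does not match deaths, permanent discontinuations or extension-only counts in patients selected for completing that study

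*SAP*

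**What the plan says.** - **Entry.** Protocol 7.1, criterion I 01, requires that the patient "completed the treatment period of a previous study of olipudase alfa with an acceptable safety profile", as judged by investigator and sponsor.
- **Exposure clock.** SAP 2.4.6.1 says "The extent of study treatment exposure will be assessed from the first infusion in the original study". The clock runs by calendar date to disposition or data cutoff, and "The total number of patient-years of exposure will also be provided". SAP 2.1.3 and 2.4.7 start the treatment epoch and on-treatment period at the same infusion. SAP 1.5 declares this as a change from Protocol 11.6.3, made to bring in the original-study data.
- **Deaths.** SAP 2.1.3.2 defines on-treatment deaths as "deaths occurring during the treatment epoch". A second category, on-study deaths, begins at consent to LTS13632.
- **Adverse events.** SAP 2.4.7.1.1 takes the safety population as the denominator for percentages and adds: "Total patient year for each group will be calculated and displayed on selected AE tables". The overview in SAP 2.4.7.1.2 covers fatal TEAEs and TEAEs leading to treatment discontinuation or study withdrawal. One of its lines leaves out original-study events. AEs, SAEs and IARs that begin after the first LTS13632 infusion are also listed separately.
- **Disposition.** In SAP 2.2 the percentage enrolled is "calculated based on the number of patients who have completed the treatment period of the original study on schedule", and enrolled means consented and meeting every enrollment criterion. Protocol 11.3 has: "Enrolled patients are defined as patients who signed informed consent forms".

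**The concern.** Long-term safety is the primary objective. For death and permanent discontinuation, I 01 makes the original treatment period event-free by selection among LTS13632 patients: anyone with such an event could not have entered. Their time in that period is nevertheless counted in the only patient-year total available. The extension-only outputs (the overview line, the listings and on-study deaths) supply counts but no patient-years to set against them. Anyone who divides one by the other will use too large a denominator and get too low a rate.

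The disposition table is where selection into the extension should become visible. As specified, it starts from patients who completed the original study, so patients who stopped early do not appear.

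**Working it through.** The documents state no patient-year total or event rate, so there is no planned figure to reproduce.

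**Inputs.** Original-study durations are 26 weeks (adult) and 64 weeks (pediatric), from SAP 2.4. Cohort sizes are 5 adults and about 20 children in Protocol 6 and SAP 1.1, but 5 and 12 in SAP 1.3 and 2.4, so both are shown. Actual extension follow-up is not given and is varied as an assumption. Protocol 6 sets at least 3 years for every pediatric patient and a maximum of 9 years.

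**Original-study time** = sum of n × weeks / 52.18 (365.25/7 weeks per year):
- 5 + 20 patients: 5 × 26/52.18 + 20 × 64/52.18 = 2.49 + 24.53 = 27.02 patient-years
- 5 + 12 patients: 2.49 + 12 × 64/52.18 = 2.49 + 14.72 = 17.21 patient-years

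**Share of pooled total** = original / (original + extension):

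| Mean extension follow-up (assumed) | 25 patients: extension / total PY | Share | 17 patients: extension / total PY | Share |
|---|---|---|---|---|
| 3 years | 75 / 102.0 | 26.5% | 51 / 68.2 | 25.2% |
| 5 years | 125 / 152.0 | 17.8% | 85 / 102.2 | 16.8% |
| 9 years | 225 / 252.0 | 10.7% | 153 / 170.2 | 10.1% |

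**Effect on a rate** = extension PY / total PY. With 25 patients this is 75/102.0 = 0.74, 125/152.0 = 0.82 and 225/252.0 = 0.89. One extension event at 3 years would read 100/102.0 = 0.98 per 100 patient-years instead of 100/75 = 1.33.

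**Which outputs are touched:**
- *Other TEAEs, pooled.* Original-study events and time are both included, so numerator and denominator match.
- *Extension-only counts.* Any rate on the pooled total is mismatched, however many patients rolled over.
- *Deaths and permanent discontinuations.* Among LTS13632 patients these can occur only after the original treatment period. The pooled rate misstates the experience of all treated patients only if someone failed to roll over.

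**Rollover.** Protocol 4.1 reports that all Phase 1b adults entered the long-term study and that none died, so there is no adult selection. For children, the amendment history (17.2.4) says DFI13803 planned about 20 patients, and Protocol 6 expects about 20 to roll over. The actual number who did not is not stated.

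**Disposition wording.** Read literally, the on-schedule condition puts a late completer, who still satisfies I 01, outside the denominator. A patient dosed and later found ineligible (foreseen in Protocol 8.1.8 and 10.4.3) belongs to the safety population in SAP 2.3.1 but not to the SAP's enrolled group, which is the denominator for the other disposition percentages. Neither SAP 1.5 nor 1.6 declares the narrower definition of enrolled.

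**The case against.** A reader might infer that the trial's death and discontinuation rates will be reported too low. The documents do not support that. Protocol 11.6.3.1.2 and SAP 2.4.7.1.1 present these events as counts and percentages of patients, which the exposure clock does not alter. The annualized rate in Protocol 11.6.3.1 concerns AE counts by dose level. Safety is descriptive, and no upper confidence limit for a zero-death result is planned, so contrasting such limits on the two clocks would criticise an output that does not exist.

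A reader might also take the share at 1 year of follow-up, 27.0/52.0 = 52%, as the size of the problem. With the 3-year pediatric minimum, and adult 3-year biopsies already analysed by April 2018 (17.2.4), that figure could apply only to an early data cut. Nor is each child who did not roll over, one in about 20, a hidden 5 percentage points: not entering the extension is neither a death nor necessarily a safety stop.

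The plan also contains real mitigation. On-study deaths start at consent, extension-only events are shown, displays are split by original study, readers are sent to the original study report, and the changed treatment period is openly declared. With full rollover, the pooled patient-years are legitimate time from first dose. The disposition table states its denominator, and excluding late completers is only one reading of loose wording.

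All of that stands. What it leaves is narrower. The extension-only counts still lack a denominator. Subtracting 26 or 64 weeks per patient gives only an approximation, because the clock is date-based and also counts any gap between studies. The one table that could show whether selection occurred does not start early enough to do so.

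**Conclusion.** The point holds as a mismatch between numerators and denominators, not as a demonstrated bias in a planned estimate. The pooled total includes about 27 patient-years (17 with the SAP's cohort sizes) in which no LTS13632 patient could have died or permanently stopped. That is about 25–27% of the total at a mean of 3 years' extension follow-up and 10–11% at 9 years. It would lower a per-patient-year reading of these events, or of extension-only counts, to about 0.74 to 0.89 of its extension-only value with 25 patients.

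These sizes rest on assumed follow-up and on nominal original-study durations. Selection bias proper would also need DFI13803 patients who did not roll over. That number is unknown, and the planning figures point to few or none. The undeclared difference in the definition of enrolled is real but matters only if an ineligible patient is dosed.

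**What to change.** - **SAP 2.4.6.1 and 2.4.7.1:** report patient-years from the first LTS13632 infusion beside the pooled total. Use them for any per-patient-year statement on deaths, TEAEs leading to treatment discontinuation or study withdrawal, and TEAEs outside the original study. Keep the pooled displays for other TEAEs, labelled as describing patients who completed the original study.
- **SAP 2.2:** begin the disposition table with all patients treated in DFI13412 and DFI13803, then those who completed, then those not enrolled with the reason. Remove the on-schedule condition from the denominator. Define enrolled by signed consent as in Protocol 11.3, or declare the change in SAP 1.5.

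The cost is SAP wording, one more patient-year column and a few disposition rows from data the sponsor should hold. The date needed already exists: SAP 2.4.6.2 counts expected infusions from the first extension infusion. The downside is a slightly longer table and less favourable rates for rare terminal events.

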6.1.2 Post treatment period

For patients completing or discontinuing/withdrawing from the study, there will be a posttreatment period consisting of an end-of-treatment (EOT) visit 2 weeks (± 7 days) after the last administered dose of study treatment and a safety follow-up phone call 30 to 37 days after the last administered dose of study treatment.

An EOT visit and a safety follow-up phone call will also apply in case the patient switches immediately after the end of study treatment to commercial treatment.

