10.3 DEFINITION OF SOURCE DATA

Source data includes all information in original records and certified copies of original records of clinical findings, observations, or other activities necessary for the reconstruction and evaluation of the trial. Source data are contained in source documents.

Source documents are original documents, data and records (eg, hospital records, clinical and office charts, laboratory reports and notes, memoranda, patient diaries or evaluation checklists, pharmacy dispensing records, recorded data from automated instruments, copies or transcripts certified after verification as being accurate and complete, microfiches, photographic negatives, microfilm or magnetic media, X-rays, patient files, and records kept at the pharmacy, at the laboratories, and at medical-technical departments) involved in the clinical study. Source documentation must be maintained to support information provided in the CRF.

All protocol-required information collected during the study must be recorded by the investigator or other study personnel in the source documentation for the study. The source documentation will be used to enter the protocol-required information into the CRF. No data should therefore be directly entered into the CRF.

10.4 HANDLING OF PATIENT TEMPORARY OR PERMANENT TREATMENT DISCONTINUATION AND OF PATIENT STUDY DISCONTINUATION

The IMP should be continued whenever possible. In case the IMP is stopped, it should be determined whether the stop can be made temporarily; permanent IMP discontinuation should be a last resort. Any IMP discontinuation should be fully documented in the source and CRF. In any case, the patient should remain in the study as long as possible.

Pregnancy will lead to treatment discontinuation in all cases. Sexually active female patients of childbearing potential and sexually active male patients who permanently discontinue must use 2 forms of contraception for at least 15 days after their last dose.

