11.6.3 Analyses of safety data

Safety assessments are described in [Section 9.1.4](#) through [Section 9.1.15](#). All safety analyses will be performed on the safety set (defined in [Section 11.4](#)). No formal inferential testing will be performed. Summaries will be descriptive in nature.

The following definitions will be applied to laboratory parameters, ECGs, and vital sign measurements.

- The potentially clinically significant abnormality (PCSA) values are defined as abnormal values considered medically important by the sponsor according to predefined criteria/thresholds based on literature review and defined by the sponsor for clinical laboratory tests and vital signs.
- PCSA criteria will determine which patients had at least 1 PCSA during the treatment period, taking into account all evaluations performed during the treatment period, including unscheduled or repeated evaluations. The number of all such patients will be the numerator for the treatment PCSA percentage.
- Treatment period: the treatment period used for quantitative analysis is defined as the time from first dose to the last dose of IMP +14 Days.

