## 1.5 MODIFICATIONS TO THE STATISTICAL SECTION OF THE PROTOCOL

In the section of statistical consideration of the Amended Clinical Trial Protocol 4 Section 11.6.3, treatment period is defined as time from first dose to the last dose of IMP +14 days. In this SAP, in order to incorporate the data from original study (ie, adult study DFI13412 or pediatric study DFI13803), the treatment period definition is changed to “the time from the first infusion of IMP (included) from original study to the end of the current study”.

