## 1.6 STATISTICAL MODIFICATIONS MADE IN THE STATISTICAL ANALYSIS PLAN

The SAP Version 2 was based on Amended Clinical Trial Protocol 1. This SAP is based on Amended Clinical Trial Protocol 4 (dated 31July 2019).

- The post-treatment period has been removed from [Section 2.1.3](#), since there is no pre-specified post-treatment period in the protocol.
- The paired t-test was used for testing change from baseline and/or percent change from baseline. Because the baseline value is highly correlated with change from baseline and/or percent change from baseline, the paired t-test has been changed to analysis of covariance with baseline included as covariates as indicated in [Section 2.4.8](#).
- The definition of common TEAE, TEAE of infection, Hypersensitivity IARs and TEAE of bleeding are updated in [Section 2.1.3.1](#).
- Analyses of adverse events by place of infusion was added to this SAP in [Section 2.4.7.1.6](#).
- Subgroup analyses for efficacy endpoints was added to this SAP for patients from DFI13803 in [Section 2.4.8.15](#).
- Patient narratives as described in [Section 2.5](#) will be created, to replace various data listings.

- For Physician's global assessment of change, the 7 categories will be converted to numeric values and summarized, as described in [Section 2.4.8.6](#).

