### ***Handling of computation of treatment duration if investigational medicinal product end of treatment date is missing***

For the calculation of the treatment duration, the date of the last dose of study treatment is reported on the last infusion page in e-CRF.

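### Exposure runs to an undefined disposition date and the on-treatment period to end of study, so time after the last infusion counts as treatment

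*SAP*

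**What the plan says.** **Exposure.** SAP 2.4.6.1: "The duration of exposure is defined as the number of weeks between first infusion in the original study and disposition date in the study". The database-lock cutoff replaces the disposition date for patients still ongoing. The same section adds: "The total number of patient-years of exposure will also be provided". Neither document defines the disposition date. For treatment duration, the missing-date note in SAP 2.6.2 points to a different date: "the date of the last dose of study treatment is reported on the last infusion page".

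**On-treatment period.** For laboratory, ECG and vital-sign data, protocol 11.6.3 defines the treatment period as "the time from first dose to the last dose of IMP +14 Days". SAP 1.5 cites that rule and replaces it with "the time from the first infusion of IMP (included) from original study to the end of the current study", so that feeder-study data can be included. SAP 2.4.7 applies the new period to all safety data, and SAP 2.4.7.1.1 uses it to define treatment-emergent events. The treatment epoch in SAP 2.1.3 ends instead on the latest date with data.

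**Post-treatment period.** SAP 1.6 says this was removed from SAP 2.1.3 "since there is no pre-specified post-treatment period in the protocol". Protocol 6.1 divides the study into a treatment and a post-treatment period. Protocol 6.1.2 describes the second: "there will be a posttreatment period consisting of an end-of-treatment (EOT) visit 2 weeks" (± 7 days) after the last dose, then a safety call at days 30 to 37. SAP 1.4 lists the same visit and call.

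**The concern.** The SAP has four different anchors for the end of treatment: disposition date, end of study, latest data date and last dose. Two programmers could follow it and derive different exposure.

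Three outputs are affected:

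- Duration of exposure and patient-years include days after the last infusion. Patient-years appear on selected adverse event tables (SAP 2.4.7.1.1).
- Laboratory, ECG and vital-sign values taken more than 14 days after the last dose count as on-treatment, including in the summaries of potentially clinically significant abnormalities. Protocol 11.6.3 would exclude them.
- The two death categories in SAP 2.1.3.2 no longer separate deaths on study drug from deaths after stopping it.

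Safety is the primary objective, so these definitions should be unambiguous.

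**Working it through.** The documents give no exposure total to reproduce, so this check compares the SAP's rule with an end at last dose + 14 days, which is one dosing interval and the protocol 11.6.3 limit.

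**Inputs**

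- SAP formula (2.4.6.1): weeks = (disposition date - first infusion date + 1)/7.
- End-of-treatment visit: day 14 ± 7, so days 7 to 21 after the last dose (protocol 6.1.2).
- Safety call: days 30 to 37 after the last dose (protocol 6.1.2).
- Sample size: about 25 (protocol 11.2, SAP 1.1). SAP 1.3 still says 17.
- Feeder-study treatment: 26 weeks for adults, 64 weeks for children (SAP 2.4).
- Treatment in this study: at least 3 years for children, at most 9 years (protocol 6).
- Assumption: the disposition date is either the end-of-treatment visit or the safety call.

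**Difference per finished patient.** With the same +1 on both sides, the difference is (days from last dose to disposition) - 14.

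- Safety call: 30 - 14 = +16 to 37 - 14 = +23 days.
- End-of-treatment visit: 7 - 14 = -7 to 21 - 14 = +7 days.

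**Total if all patients have finished and disposition is the call**

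- 25 patients: 25 × 16/365.25 = 1.10 to 25 × 23/365.25 = 1.57 patient-years.
- 17 patients: 0.74 to 1.07 patient-years.

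Patients still ongoing are cut at the database-lock date and add little, so these totals are upper limits.

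**Relative size.** Taking 52 weeks per year, exposure to last dose + 14 days is (7 × weeks + 15) days:

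| Assumed time on drug | Days | +16 days | +23 days |
|---|---|---|---|
| 64 + 156 = 220 weeks | 1555 | 1.03% | 1.48% |
| 26 + 468 = 494 weeks | 3473 | 0.46% | 0.66% |
| 64 + 468 = 532 weeks | 3739 | 0.43% | 0.62% |

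**Assumed case: drug stopped, patient stays in the study.** With 104 weeks on drug, exposure to last dose + 14 days is 106 weeks. With 26, 52 or 104 weeks off drug, the SAP rule gives 130, 156 or 208 weeks. The excess is 24/106 = 22.6%, 50/106 = 47.2% or 102/106 = 96.2%, for that patient only.

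**Deaths.** In SAP 2.1.3.2, on-treatment runs from the first infusion in the feeder study to the latest data in this one. On-study runs from consent in this study to its end. Consent comes after the first feeder-study infusion, so any on-study death is also on-treatment, however long after the last infusion it occurs.

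**The two stated reasons.** Including feeder-study data (SAP 1.5) requires an earlier start; it says nothing about the end. The statement in SAP 1.6 is contradicted by protocol 6.1 and 6.1.2 and by the visit and call in SAP 1.4.

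**The case against.** A good deal can be said for the plan.

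- **Adverse events and deaths.** A reader might infer that the protocol sets a 14-day limit for these too. It does not. In 11.6.3 the window is among definitions applied to laboratory, ECG and vital-sign data, and 11.6.3.1 and 11.6.3.1.2 set no such limit. Counting events through the safety call adds events rather than hiding them. This stands.
- **Cause.** A reader might infer that the misstatement in SAP 1.6 explains all the longer windows. It is given only for removing the period from SAP 2.1.3. SAP 1.5 has its own reason, and 2.4.6.1 gives none. This stands.
- **Version.** The SAP follows Amended Protocol 4, and the protocol supplied is 07. But SAP 1.4 carries the visit and call, SAP 1.5 cites the 14-day rule from version 4, and the 07 change log records 6.1.2 as updated, not added. This does not rescue SAP 1.6.
- **Denominator.** A reader might infer that adverse event percentages are diluted. SAP 2.4.7.1.1 divides by the safety population; patient-years are only displayed. Protocol 11.6.3.1 mentions an annualized rate, but the SAP specifies no such calculation. This stands.
- **Long off-drug follow-up.** Protocol 10.4 says "In any case, the patient should remain in the study as long as possible". The operative text for stopping (protocol 6.1.2, 8.1.8, 10.4.3) provides only the closing assessments and the call, and the flow charts have no longer off-drug schedule. A patient off drug for a year is therefore an assumed case. A patient who switches at once to commercial product is not off drug, though no longer on study treatment.
- **Safeguards.** SAP 2.4.7.1.1 derives each event's start day relative to the last infusion. Deaths and serious events get narratives (SAP 2.5). SAP 2.4.7 also says safety data are reported up to treatment withdrawal plus adverse event follow-up. This softens the problem but leaves the definitions in conflict. The note in SAP 2.6.2 mainly says where a date is recorded, so it is weak evidence of a contradiction on its own.

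**Conclusion.** The point holds as a fault of definition with a small expected numerical effect. The SAP ends exposure on an undefined date, moves the end of the on-treatment period without a reason that supports it, and misstates the protocol on the post-treatment period. It does not follow that adverse event percentages are biased, that the protocol requires a 14-day limit for adverse events or deaths, or that large amounts of false exposure are expected.

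The range of +16 to +23 days per finished patient (at most about 1.1 to 1.6 patient-years, roughly 0.4-1.5%) assumes that disposition is the safety call, and the total assumes that all 25 patients finish. If disposition is the end-of-treatment visit, even the sign is not fixed. Only a patient who stops drug and stays in the study would show a larger excess, and the documents do not say that any will. The loss of the distinction between deaths on and after treatment does not depend on these assumptions.

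**What to change.** 1. In SAP 2.4.6.1, define exposure as (last infusion date - first infusion date + 14)/7 weeks, and use the cutoff date only for patients still being infused. This drops the SAP's +1, so each result is one day shorter than in the comparison above.
2. For laboratory, ECG and vital-sign abnormalities, end the window at last infusion + 14 days as in protocol 11.6.3, and keep the start at the first infusion in the feeder study. End-of-treatment values from days 15 to 21 then fall outside the window and should remain in the listings.
3. Keep adverse events collected through the safety call in the tables, but show adverse events and deaths after last infusion + 14 days in a separate post-treatment row.
4. Delete the incorrect statement in SAP 1.6, and align SAP 2.1.3, 2.1.3.2, 2.4.6.1, 2.4.7 and 2.6.2.

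The cost is one derived date, slightly smaller patient-years and one extra table row. No new data are needed.
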